Comparator products:	Placebo		
dose:	Not applicable		
mode of administration:	Subcutaneous injection		
Duration of treatment:	52 weeks		

Name of company:		Boehringer Ingelheim	
Name of finished product:		Not applicable	
Name of active ingredient:		BI 655064	
Protocol date: 29 Oct 2015	Trial number: 1293.10		Revision date: 07 SEP 2018
Endpoints	
Primary endpoint : Proportion of patients with Complete Renal Response at week 52
 
Secondary endpoints :
 
Proportion of patients with Complete renal response at week 26
 
Proportion of patients with Partial renal response at week 26 and 52
 
Proportion of patients with Major renal response at week 26 and 52
		
Safety criteria:	Physical examination, vital signs (BP, PR), weight, 12-lead ECG, laboratory tests, adverse events and tolerability		
Statistical methods:	The primary objective is to define a suitable dose for BI 655064 regarding efficacy and safety for further pivotal testing in Phase III. For this purpose, a multiple comparison procedure with modelling (MCPmod) approach is considered. The primary endpoint is Complete Renal Response after 52 weeks of treatment. Comparisons between treatment groups will be exploratory in nature and based on the numerical comparison of the respective response rates including confidence intervals when appropriate.		

FLOW CHART

Trial Periods	Screening	Randomised Treatment Period (week 0 – 26)											
		1	2	2.1	2.2	3	4	5	6	7	8	9	10
Visit	1	2	2.1	2.2	3	4	5	6	7	8	9	10	11
Day	-28 to -	1	2 ¹	3 ¹	8	15	29	43	57	85	113	148	18
Week	-4 to -1	0			1	2	4	6	8	12	16	21	26
Time window for visits (days)	N.A.	±0	±0	±0	±1	±1	±2	±2	±3	±3	±5	±5	±3
Check of Eligibility	X	X											
Informed Consent	X												
Med. History / Demographics	X												
Physical Examination ²	X ^c	X ^c			X ^t	X ^t	X ^t	X ^t	X ^t	X ^c	X ^t	X ^t	X ^c
12-Lead Resting ECG		X					X			X			X
Inclusion/Exclusion Criteria	X	X											
Randomisation		X											
Administer BI 655064/placebo ³		X			X	X	X	X	X	X	X	X	X
Administer Methylprednisolone 500mg i.v. (SOC I) ¹		X	X	X									
Start oral glucocorticoids ⁴				X									
Administer MMF 2-3g/day													
Dispense treatment and instructions for home admin ⁵						X	X	X	X	X	X	X	X
Assess compliance							X	X	X	X	X	X	X
Assess for Adverse Events		X	X	X	X	X	X	X	X	X	X	X	X
Concomitant Therapy	X	X	X	X	X	X	X	X	X	X	X	X	X
Safety Laboratory Tests ⁶	X	X			X	X	X	X	X	X	X	X	X
2 x 24h collection of urine		X											X

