3. DESCRIPTION OF DESIGN AND TRIAL POPULATION

3.1 OVERALL TRIAL DESIGN AND PLAN

This study will be randomized, parallel-design, dose-ranging, placebo-controlled, double-blind, multi-centre and multi-national. A total of up to approx. 120 male and female patients with active lupus nephritis will be randomized in this trial in about 22 countries. There will be three parallel BI 655064 dose groups (approx. 20, 20 and 40 patients) and one placebo dose group (approx. 40 patients). The patients will be randomized 1:1:2:2 to these dose groups. Randomisation will be done with stratification by ethnicity (Asians vs Non-Asian) and proteinuria at screening $<3\text{g/day}$ or $\geq 3\text{g/day}$ (respectively UP/UC <3 or UP/UC ≥ 3). All patients will receive standard of care (SOC) treatment for lupus nephritis, consisting of a 6 month initial phase with 2-3 g MMF/day starting with high dose steroids which will be tapered down to 10 mg prednisone equivalent within 12 weeks after randomization (Refer to [section 4.2.1](#)), followed by a second phase (from week 26 on) with 1-2 g MMF/day in combination with steroids ≤ 10 mg prednisone equivalent/day. BI 655064 will be administered subcutaneously at 3 different doses. For the first 3 weeks the patients will receive two parallel injections/week on the same day of BI 655064 and/or placebo. Then the patients will receive one injection/week of BI 655064 or placebo for up to 52 weeks (12 months). Patients in the placebo dose group will receive only injections of placebo to BI 655064.

The primary endpoint (complete renal response as defined in [section 5.2](#)) will be assessed at 52 weeks. Patients with at least a partial response at week 52 will be offered to enter a maintenance trial (1293.13).

[figure not shown]

Figure 3.1: 1: Outline of trial design

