4.2 CONCOMITANT THERAPY, RESTRICTIONS, AND RESCUE TREATMENT

4.2.1 Rescue medication, emergency procedures, and additional treatment(s)

There are no special emergency procedures to be followed.

Background medication:

All patients will receive standard of care (SOC) treatment for lupus nephritis based on MMF:

SOC Initial phase (week 1 – 26):

- MMF: patients who are already on MMF of 2 g/day or a maximum of 3 g/day should stay at same MMF dose, provided that they have tolerated it well. Patients who start treatment with MMF or patients with a dose <2g/day should be increased to a stable MMF dose of 2g/day. It is recommended not to increase MMF above 2g/day to reduce the risk of severe side-effects of MMF. In case of side effects related to MMF, a MMF dose < 2g/day is allowed.
- AND glucocorticosteroids (GC) (methylprednisolone, recommended 500mg pulse IV for 3 days) followed by oral glucocorticosteroids, tapering to 10mg prednisone equivalent/day within 12 weeks. Tapering of steroids should follow the tapering schedule in [Appendix 10.1](#). Patients who have had already a course of IV steroids (up to a total dose of maximum 3g if it had been considered necessary by the investigator) within 6 weeks prior to randomization should not necessarily repeat it depending on what they received. They should only have necessary pulses to reach a total of 1.5g IV steroids. E.g : if they have already received 2 pulses of 500mg, they will just receive one additional pulse. If they have already had 3 *500 mg, they simply do not repeat any IV pulse. If considered necessary by the investigator, a maximal dose of 1000 mg methylprednisolone per day for up to 3 days (maximal 3000mg) is acceptable.

SOC week 26 – 52:

- Mycophenolate mofetil (MMF) 1 to 2 g/day stable + low-dose (≤ 10 mg/day) prednisone-equivalent

From week 26 only, in case of side effects: MMF may be reduced to 1g/day or in case of non tolerability, patients could be switched to Azathioprine (AZA) 2mg/kg/day + (≤ 10 mg/day) prednisone-equivalent low-dose daily.

In patients who experience a worsening or a flare, the investigator is allowed to increase the steroid dose for the patient. These patients are allowed to continue treatment with BI 655064 until week 52..

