6.2.2 Treatment period(s)

For details description of trial procedures during the treatment period, refer to [Flow Chart](#). Only additional critical information is listed below.

Eligible patients will be randomised to receive the first dose of study medication at Visit 2. Each patient can only be randomised once in the trial via IRT.

Visit 2, 2.1, 2.2: drug administration:

The induction phase with SOC might have started for some patients already before the randomisation in the trial.

- MMF: if the patient is naïve with MMF or has received a dose < 2g/day, he will start receiving 2-3g/day MMF at visit 2
- Intravenous Glucocorticoids: patients who have not yet received any high dose pulse IV steroids will receive 500 mg methylprednisolone for 3 days (visits 2, 2.1, 2.2). If considered necessary by the investigator, a maximal dose of 1000 mg methylprednisolone for 3 days is acceptable. In case the patient had already received pulse steroids (max 3g total within last 6 weeks) he will receive additional IV steroids only to reach 1.5g total. If the 1.5 g is reached the visit 2.1 and 2.2 are not necessary.

The investigator will prescribe daily oral steroids starting the day after the last IV steroids. Refer to [section 4.2.1](#). This should be tapered down to 10 mg prednisone equivalent within 12 weeks.

drug injection:

For all other weekly injection, this can either be administered on-site or at home by the patient.

Urine collection:

At visit 2 and 11 and 16, 2 times 24h collection of urine will be performed. The patient will be given instructions and material to allow collection of urine during 2 days in the week preceding the visit. At other time points, proteinuria will be assessed by spot urine.

Drug administration:

According to the [Flow Chart](#) the patients will be receiving the syringes necessary for the next week(s) injection at home between two visits. The patients will be given instructions for injection and treatment number, and a diary to record the exact date and time of injection

At any visit, should a decision be made to discontinue the patient from study medication, please complete EOT visit.

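### Protocol 4.2.1 and 6.2.2 give different MMF starting instructions for MMF-naive or under-dosed patients, and only 4.2.1 carries the safety advice

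*Protocol*

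**What the plan says.** Protocol 4.2.1, which sets out the background therapy for weeks 1 to 26, separates two kinds of patient. Those who arrive on an adequate dose and tolerate it keep it: "patients who are already on MMF of 2 g/day or a maximum of 3 g/day should stay at same MMF dose". Those who are new to MMF or below that range are handled differently: "Patients who start treatment with MMF or patients with a dose <2g/day should be increased to a stable MMF dose of 2g/day". The section then advises: "It is recommended not to increase MMF above 2g/day to reduce the risk of severe side-effects of MMF".  A dose below 2 g/day is allowed if there are MMF side effects.

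Protocol 6.2.2, the visit-level instruction for Visits 2, 2.1 and 2.2, addresses the second kind of patient directly. For a patient who is new to MMF or below 2 g/day, it says that "he will start receiving 2-3g/day MMF at visit 2". It does not repeat the advice against going higher.

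Two summary statements give the same range without distinguishing patients by prior MMF use. Protocol 3.1 describes standard of care as "consisting of a 6 month initial phase with 2-3 g MMF/day", and the flow chart has the row "Administer MMF 2-3g/day". Protocol Table 4.2.2.1 sets the permitted maximum for weeks 0 to 26 at 3 g/day. In the SAP, important protocol deviation D3 flags MMF above 3 g/day up to week 26.

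**The concern.** Sections 4.2.1 and 6.2.2 give the same patients different starting instructions. One gives a single dose and recommends against exceeding it, for a stated safety reason. The other gives a range whose upper part is what the first advises against.

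A site could plausibly act on 6.2.2 alone. That section presents itself as the critical additional information for the treatment visits. Its MMF bullet does not point to 4.2.1; the cross-reference to 4.2.1 in that part of the text follows the oral steroid instruction.

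What is at stake is mainly safety. Protocol 2.3 associates MMF with a higher risk of infection and of blood, lymphatic and gastrointestinal effects. Protocol 4.2.1 refers to side effects known to occur at higher MMF doses. Protocol 5.3.5.1 describes BI 655064 itself as immunosuppressive and lists severe infections among the adverse events of special interest. A patient may thus receive, on top of a second immunosuppressant, more MMF than the protocol's own treatment section recommends, without any departure from the visit instructions.

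**Working it through.** No sample size, power or error rate enters this point. The check compares the current text and adds one small calculation.

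**1. Are the two sections about the same patients?** Yes. Both name patients new to MMF and patients below 2 g/day. Reading the 2-3 g/day in 6.2.2 as covering only patients who arrive on a higher dose does not work, because 6.2.2 attaches the range to the naive and under-dosed group.

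**2. Is this current text?** Yes. Both statements stand in the body of the protocol, not in the amendment log.

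**3. Where do the instructions agree and differ for this group?**

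| Place | Starting MMF dose | Advice on going above 2 g/day |
|---|---|---|
| 4.2.1 | stable 2 g/day | recommended against, safety reason given |
| 6.2.2 | 2 to 3 g/day | none stated |
| 3.1 and flow chart | 2 to 3 g/day, all patients | none stated |
| Table 4.2.2.1 | maximum 3 g/day | none stated |

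A site that gives 2 g/day satisfies every row. The conflict covers doses above 2 and up to 3 g/day.

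**4. How large can the gap be for one patient?**

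- Daily gap: 2 − 2 = 0 g/day at the bottom of the 6.2.2 range and 3 − 2 = 1 g/day at the top. As a share of 2 g/day, 1 / 2 = 50%.
- Length of the initial phase: 26 × 7 = 182 days.
- Cumulative dose: 2 × 182 = 364 g against 3 × 182 = 546 g, a gap of 546 − 364 = 182 g.

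The 182 g is a ceiling. It requires the top of the range from Visit 2, with no reduction, for the whole phase.

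**5. How many patients are affected?** This cannot be computed. The documents do not give the share who enter naive or below 2 g/day, nor how many sites would go above 2 g/day. The number could be zero.

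**6. Does SAP D3 conflict with the protocol?** No. D3 flags doses above 3 g/day up to week 26, and Table 4.2.2.1 permits up to 3 g/day in that period. The two limits match.

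**The case against.** The strongest case on the other side is that nothing here is a hard contradiction. The texts share 2 g/day. Section 4.2.1 speaks of what should be done and what is recommended, which is advice. Table 4.2.2.1 sets the only outright maximum, and 6.2.2 stays within it. On that reading 6.2.2 gives the permitted range and 4.2.1 the preferred dose inside it. Much of this stands, and it limits the point to a conflict of instructions. It does not remove the conflict: 6.2.2 says what these patients will receive, does not mark its upper part as discouraged, and its MMF bullet does not send the reader to the section that does.

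It is also fair that 3.1 and the flow chart are weak evidence. They summarise a mixed population that includes patients whom 4.2.1 keeps on up to 3 g/day, so the range is correct for the whole group. The mismatch lies between 4.2.1 and 6.2.2.

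A reader might infer three stronger claims. The documents do not support them.

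- **That uneven MMF dosing distorts or blurs the efficacy comparison.** Allocation is randomised and double-blind, so no systematic difference between arms follows, although chance imbalance is possible with arms of 20 and 40. The added-noise argument is weak as well. Complete renal response is binary. If independent patients have individual response probabilities pᵢ with mean p, the variance of one outcome is E[pᵢ(1 − pᵢ)] + Var(pᵢ) = p(1 − p), whatever the spread of pᵢ. With 1 to 2 patients planned per site, clustering by site adds little. The primary endpoint is read at week 52, and 4.2.1 puts all patients on 1 to 2 g/day MMF, or azathioprine if MMF is not tolerated, from week 26.
- **That SAP D3 is defective because it would not flag a naive patient started above 2 g/day.** D3 follows the permitted maximum. Departing from a recommendation is not normally an important deviation. Because D3 can lead to exclusion from the per protocol set, tightening it could turn advice into an exclusion rule.
- **That toxicity in the trial has been shown to depend on which section a site followed.** The protocol gives a reason for concern, but neither document contains data on it.

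**Conclusion.** The point holds as a safety-relevant inconsistency between Protocol 4.2.1 and 6.2.2 in the MMF starting instruction for patients who are naive or below 2 g/day. Its size for one patient is 0 to 1 g/day above 2 g/day, up to 50%, and at most 182 g over the 26-week initial phase. The number of patients affected is unknown.

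The conclusion rests on two assumptions: that some patients enter naive or under-dosed, which 4.2.1 and 6.2.2 both provide for, and that some sites may work from the visit instructions without consulting 4.2.1. It does not extend to bias, to a loss of precision on the primary endpoint, or to an error in the SAP. No view is taken on which instruction is right.

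**What to change.** Reconcile 4.2.1 and 6.2.2 so that both give one starting instruction for patients who are naive or below 2 g/day, with the same position on higher doses. Add a reference to 4.2.1 in the MMF bullet of 6.2.2 and in the flow chart row. In 3.1, make the existing reference to 4.2.1, which now follows the steroid taper, cover MMF as well. The sponsor's clinical team decides which instruction stands. Leave SAP D3 as it is unless that decision changes the maximum in Table 4.2.2.1.

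The cost is a few lines in a protocol amendment and a notice to sites, with no effect on sample size or analysis. The benefit to patients depends on timing. The revised SAP (17 August 2020) was written after the interim analysis, which Protocol 7.4 places after all patients have completed 26 weeks. By then every starting dose had been given, so a late correction would clarify the record but could not change anyone's treatment.

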6.2.3 Follow Up Period and Trial Completion

6.2.3.1 End of Treatment (EOT) Visit:

All patients will be asked to return for the EOT visit within 7 days from the last dose of study medication (either at week 52 for completers, or when a patient prematurely discontinues the drug). For details description of the trial procedures at EOT, refer to the [Flow Chart](#). 2 times 24h collection of urine has to be organized for this visit.

For patients that are eligible to participate in the extension trial 1293.13, the EOT visit will occur on the same day as the Visit 1 of the roll-over trial.

6.2.3.2 Follow-Up (FU) and End of Study (EOS) Visit:

After the end of treatment visit, patients who completed the 52 weeks treatment but are not eligible for the extension trial will return for a follow-up visit (after 4 weeks) and an EOS visit, 8 weeks after EOT.

Patients who are eligible for the extension trial will not have to complete the FU visit nor the EOS visit, but only the trial completion page will have to be completed.

During FU and EOS visits, the investigator will continue to follow-up on AEs that are not yet recovered. At EOS visit, the investigator needs to confirm whether the AEs are sufficiently followed up and provide documentation in the patient's medical records and on the eCRF.

For details description of the trial procedures at FU and EOS visits, refer to the [Flow Chart](#).

6.2.3.3 Continuation of the study for patients who withdrew drug prematurely (before completion of the 52 weeks treatment):

In case a patient has to discontinue the trial drug, prior to having completed the 52 weeks treatment (i.e., prior to visit 16), he will be invited to attend a subset of visits as originally planned until and including visit 16: visit 5 (week 4), visit 8 (week 12), visit 11 (week 26), visit 14 (week 40) and an end of study visit at 52 weeks. During these visits, the patient should undergo selected examinations: physical examination, AE and CT collection, serum creatinine and spot urine test to assess the renal function. Other safety laboratory tests, PK sample, ADA, soluble protein biomarkers and anti-ds-DNA and complement will be collected at all visits until up to 12 weeks after End of Treatment. If the next FUP visit is planned more than 12 weeks after EOT, please have all optional tests performed at least once in the FUP period: i.e. if the patient EOT is V11 (W26), the next visit will be V14 (week 40): optional tests must be done at week 40, even if the time between week 26 & 40 is >12 weeks.

The visits may continue even though the patient will be allowed to participate in another investigational study after his withdrawal (discontinuation plus 28 days). The need for visits in case of premature drug withdrawal will be explained to the patients. In case the patient discontinued more than 8 weeks before week 52, no further follow up would be needed after week 52. In case the patient discontinued less than 8 weeks before week 52, the last follow-up visit will be 8 weeks +/- 5 days after discontinuation. In case the patient does not show-up at these visits, vital status information will be sought at planned EOS visit.

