3. PK samples will be collected before study medication administration on these days if the visit date coincides with a day of injection; therefore study medication should be administered on site in that case. If the visit does not correspond to an injection day, the PK sample will be taken at anytime during the visit. Exact date and time of sampling should be recorded. See [Section 5.4](#)
4. Oral glucocorticoids have to be started on day 4 (or day 1 if IV steroids were already received) and tapered to 10mg prednisone equivalent within 12 weeks.
5. Starting from week 2, patients have to administer the injections with BI 655064/placebo by themselves always 7 days after the previous dose.
6. Safety lab tests : details of tests is given in [section 5.3.3](#)
7. Pregnancy test will be performed in women of childbearing potential every 4 weeks. A serum pregnancy test will be performed at screening visit. Urine dipstick tests will be done during the screening phase (8-10 days after the first test) and immediately before starting medication. It will be repeated at visits every 4 weeks and will be provided for at home pregnancy testing as soon as visit intervals are > 4 weeks,. In case of a positive urine pregnancy test result, a blood sample for serum pregnancy test will be drawn for confirmation. Only those females with a negative pregnancy test will receive study medication and will be allowed to start treatment with MMF
8. Will be measured in serum and urine
9. Questionnaires should be completed in the following order: LupusPRO, SF-36, FACIT-F, before any other visit assessment
10. EOT visit has to be carried-out for all patients when they stop treatment. At week 52, patients who reach at least partial response (based on values obtained at week 46) will be offered to enter a maintenance trial (trial 1293.13). Patients who stopped treatment before week 52 will not be allowed to participate in the maintenance trial.
11. Follow up visits to be performed after end of treatment except for patients entering the maintenance trial 1293.13 and patients who have withdrawn drug prematurely
12. For randomized patients leaving the study before the planned EOS, their vital status should be collected at week 60

TABLE OF CONTENTS

TITLE PAGE	1
CLINICAL TRIAL PROTOCOL SYNOPSIS	2
FLOW CHART	5
TABLE OF CONTENTS	9
ABBREVIATIONS	12
1. INTRODUCTION.....	15
1.1 MEDICAL BACKGROUND	15
1.2 DRUG PROFILE	16
2. RATIONALE, OBJECTIVES, AND BENEFIT - RISK ASSESSMENT	18

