5.3.6 Adverse event collection and reporting

AE Collection

The following must be collected and documented on the appropriate eCRF by the Investigator:

- From signing the informed consent onwards through the Residual Effect period (REP), until trial completion, all AEs (serious and non-serious), and all AESIs.

[figure not shown]

Figure 5.3.6:1 AE collection

The REP is defined as 50 days after the last trial medication application. All AEs which occurred through the treatment phase and throughout the REP will be considered as on treatment please see [section 7.3.4](#). Events which occurred after the REP will be considered as post treatment events.

After the last per protocol contact the Investigator does not need to actively monitor patients for AEs. However, if the Investigator becomes aware of SAEs or AESIs that occurred after the last per protocol contact, the SAEs and AESIs should be reported by the Investigator to the Sponsor if considered relevant by the Investigator.

AE reporting to sponsor and timelines

The Investigator must report SAEs, AESIs, and non-serious AEs which are relevant for the reported SAE or AESI, on the BI SAE form via fax immediately (within 24 hours) to the Sponsor's unique entry point (country specific contact details will be provided in the ISF). In specific occasions the Investigator could inform the Sponsor upfront via telephone. This does not replace the requirement to complete and fax the BI SAE form.

For Japan: All SAEs and AESIs must be reported immediately to the head of the trial site. With receipt of any further information to these events, a follow-up SAE form has to be

provided. For follow-up information the same rules and timeline apply as for initial information.

Information required

For each AE, the Investigator should provide the information requested on the appropriate (e)CRF pages and the BI SAE form, e.g. onset, end date, intensity, treatment required, outcome, seriousness, and action taken with the investigational drug(s). The Investigator should determine the causal relationship to the trial medication, and any possible interactions between the investigational drug and a Non-Investigational Medicinal Product.

The following should also be recorded as an (S)AE in the (e)CRF and SAE form (if applicable):

- Worsening of the underlying disease or of other pre-existing conditions

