6.7 BASELINE, TIME WINDOWS AND CALCULATED VISITS

Study day will be calculated relative to the date and time of the first dose of double-blind randomised treatment. The day prior to the start of double-blind randomised treatment will be ‘Day -1’ and the day of the start of double-blind randomised treatment will be ‘Day 1’; therefore ‘Day 0’ will not exist.

Unless otherwise specified, baseline is defined as the latest time-point on or before the date of the first randomised treatment administration (the date of the first dose is acceptable because the first dose of medication is to be taken in clinic on the day of randomisation AFTER all

Proprietary confidential information © 2020 Boehringer Ingelheim International GmbH or one or more of its affiliated companies

baseline assessments have been made.) If there is no measurement for a particular variable on or before the date of first randomised treatment administration then no baseline will be derived for that variable.

The following visit labels will be used in all tables & graphics. As specified in the CTP, EOT refers to the End of Treatment visit. EOS is the End of Study visit. FU is Follow Up.

For discontinued patients (only):

EOT = 'EOT'

For completed patients who do not roll over to trial 1293.13:

Week 52='Week 52/ EOT'

Week 56='FU'

Week 60='EOS'

For completed patients who roll over to trial 1293.13:

Week 52='Week 52/ EOT'

For patients who discontinue trial drug but continue participation in trial:

EOT='EOT'

Visit 5='Visit 5/FU'

Visit 8='Visit 8/FU'

Visit 11='Visit 11/FU'

Visit 14='Visit 14/FU'

EOS ='EOS/FU'

Visit labels containing 'Visit' or 'FU' occurred after the EOT visit; patient was not on drug for these visits.

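### Protocol 6.2.3.2 waives both follow-up visits for completers eligible for the extension, but the flow chart, section 8.6 and the SAP waive them only for those who enter it, so an eligible patient who declines has conflicting instructions

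*Protocol*

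**What the plan says.** **Who attends weeks 56 and 60.** Protocol 6.2.3.2 requires the visits of one group: "patients who completed the 52 weeks treatment but are not eligible for the extension trial will return for a follow-up visit (after 4 weeks", plus an end-of-study visit 8 weeks after end of treatment (EOT). For the other group it says "Patients who are eligible for the extension trial will not have to complete the FU visit nor the EOS visit"; only the trial completion page is filled in.

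Flow chart footnote 11 draws the line elsewhere: "Follow up visits to be performed after end of treatment except for patients entering the maintenance trial 1293.13 and patients who have withdrawn drug prematurely". Its second exemption covers early withdrawals, who have their own schedule in 6.2.3.3. Protocol 8.6 defines the end of the trial by completed follow-up or actual entry into the extension. SAP 6.7 assigns the week-56 and week-60 labels under the line "For completed patients who do not roll over to trial 1293.13".

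**Who may enter.** Footnote 10 offers the extension at week 52 to "patients who reach at least partial response (based on values obtained at week 46"). Section 3.1 says "Patients with at least a partial response at week 52 will be offered to enter a maintenance trial (1293.13").

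**What the safety analysis expects.** Protocol 5.3.6 sets a residual effect period (REP) of 50 days after the last dose and requires adverse events (AEs) to be collected through it. The same section adds: "After the last per protocol contact the Investigator does not need to actively monitor patients for AEs". SAP 6.1 assigns AEs and laboratory data to the treatment period up to last dose plus 50 days. It passes new or worsening events to 1293.13 only once a patient has rolled over and been dosed there.

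**The concern.** The extension is an offer, so eligible completers who decline are a foreseeable group. They take no more study drug, and their REP events belong to this trial because SAP 6.1 has no other trial to give them to. Footnote 11 brings them back at weeks 56 and 60. Section 6.2.3.2, the section a site would consult on follow-up, closes them out at EOT.

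If 6.2.3.2 is followed, the SAP reports a 50-day treatment-emergent window that was barely observed in these patients. The residual-effect events of interest include severe and opportunistic infections and thrombosis, all listed as AEs of special interest (AESIs). The scheduled urine pregnancy tests at weeks 56 and 60 also drop out, although inclusion criterion 1 requires contraception until 50 days after stopping MMF and study drug.

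The result is also uneven. Under 6.2.3.3, a patient who stops drug less than 8 weeks before week 52 is followed until 8 weeks after stopping. A full completer who is eligible but declines would have no visit after EOT.

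**Working it through.** **Inputs.** Last planned dose at week 51 (protocol Table 4.1.4:1). EOT on day 365 ± 3, follow-up on day 393 ± 5 and end of study on day 421 ± 5 (flow chart). EOT within 7 days of the last dose (6.2.3.1). REP of 50 days (5.3.6, SAP 6.1).

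**Step 1: reproduce the plan's visit days.** Day = 7 × week + 1. Weeks 52, 56 and 60 give 365, 393 and 421, as in the flow chart. Week 51 gives day 358, so the REP ends on day 358 + 50 = 408.

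**Step 2: unobserved REP if EOT is the last contact.** Unobserved days = 50 − (EOT day − last-dose day).

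| EOT timing | Gap (days) | Unobserved (days) | Share of REP |
|---|---|---|---|
| Day 365 | 7 | 43 | 86% |
| Day 362 (−3) | 4 | 46 | 92% |
| Day 368 (+3) | 10 | 40 | 80% |
| Within 7 days of last dose | 0 to 7 | 43 to 50 | 86% to 100% |

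Under the 7-day rule, 43 days is the least that can be lost.

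**Step 3: the same patient under footnote 11.** Follow-up falls 393 − 358 = 35 days after the last dose, and end of study 421 − 358 = 63 days after it. At the early edge of its window, end of study is on day 416, which is 58 days after the dose and past day 408. No REP day is left uncovered.

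**Step 4: how many patients.** The documents give no decline rate; 10–30% is an assumption.

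- Overall: protocol 2.1 puts standard-of-care response at 20–30% complete plus about 20% partial, so 40–50% of 120 = 48 to 60 eligible. Decliners: 0.10 × 48 = 4.8 to 0.30 × 60 = 18.
- Placebo: 25% complete (Table 7.7:1) + 20% partial = 45%; 0.45 × 40 = 18 eligible; decliners 1.8 to 5.4.
- 240 mg: 44% complete (Table 7.7:1) + 20% partial (assumed equal to placebo) = 64%; 0.64 × 40 = 25.6 eligible; decliners 2.6 to 7.7.
- Difference: 2.6 − 1.8 = 0.8 to 7.7 − 5.4 = 2.3 patients.

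**Step 5: share of each arm's at-risk time.** The window runs about 408 days per patient, so 43 days is 43/408 = 10.5% of it. For 240 mg, 2.6 to 7.7 patients of 40 × 10.5% = 0.7% to 2.0% of the arm's window. For placebo, 1.8 to 5.4 of 40 × 10.5% = 0.5% to 1.4%. The gap is about 0.2 to 0.6 percentage points.

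**The case against.** The best defence is that *eligible* is loose wording for *entering*. Section 6.2.3.1, just above, places EOT for eligible patients on the day of the extension's first visit, which can be true only of those who take up the offer. Section 6.1 asks for follow-up at 4 and 8 weeks after end of treatment and mentions no exemption. If 1293.13 requires signed consent for eligibility, as this trial does, a decliner would not be eligible and 6.2.3.2 would require the visits. This reading is plausible, but the text does not state it and the extension's criteria are not in the documents. A site has only the written rule.

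It is also fair that the loss is not total. Section 5.3.6 asks for AE collection through the REP. Footnote 12 asks for week-60 vital status in patients who leave before the planned end of study. Relevant serious AEs and AESIs that the investigator learns of are still reportable, and persisting events must be followed up. The laboratory loss is limited too: Table 5.3.3:1 repeats most blood tests after EOT only for significant findings, so the scheduled items lost are mainly spot protein/creatinine, urine sediment and the end-of-study immunology. A reader might infer that nobody would detect any event in these patients; the documents do not support that.

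A reader might also infer that the safety comparison is tilted in the drug's favour, because responders are the ones exempted. The direction is possible, but the size in steps 4 and 5 is small, rests on an unsourced decline rate, and enters tables that protocol 7.3.4 describes as descriptive. Most response-dependent shortening of the window comes from patients who roll over. That is part of the design and no rewording of 6.2.3.2 would change it.

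**Conclusion.** The contradiction is real and lies in current text: for an eligible completer who declines, 6.2.3.2 gives one instruction and footnote 11, 8.6 and SAP 6.7 imply the opposite. The waiver in footnote 11 is not confined to entrants, since early withdrawals are also exempt there; the conflict concerns completers only.

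Where 6.2.3.2 is followed literally, most of the REP goes without active follow-up in each such patient. That conclusion rests on the visit calendar and needs no outside assumption. How many patients this affects is unknown: about 5 to 18 of 120 on the assumed decline rates, with a between-arm difference of about 1 to 2 patients per 40-patient arm. This is a gap in safety capture that should be closed, and not evidence of a material bias between arms.

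The week-46 versus week-52 wording is a minor side point. Footnote 10 gives the operational detail and section 3.1 is an overview, but as written they do not name the same visit for the response that opens the extension.

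**What to change.** In 6.2.3.2, replace the eligibility wording with *entering* and *not entering* the extension trial, in line with footnote 11, 8.6 and SAP 6.7. The same edit to the same-day sentence in 6.2.3.1 would remove the remaining ambiguity. AE collection through the REP then covers every completer who receives no further study drug. Reconcile footnote 10 and section 3.1 on which visit's values determine the extension offer; which visit that should be is for the sponsor to decide.

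The edit is a few words, and both visits are already in the flow chart, so no procedure is added. The real cost is administrative: under section 8.1 amendments need ethics and authority approval, here in about 22 countries and 80 to 100 sites, so the change is best carried with another amendment. If patients have already been closed out under 6.2.3.2, the report should state by arm how many completers neither entered 1293.13 nor attended weeks 56 and 60, so that the 50-day summaries can be read accordingly.
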